4. STUDY POPULATION

4.1 Participant flow through trial

Participant flow through the trial will be presented using a CONSORT diagram, see Example Figure 1. Information will be provided on numbers and reasons for: screened patients not being eligible; eligible patients not being randomised; participants found to be ineligible after randomisation; participants deviating from allocated treatment; participants not evaluable for the primary endpoints and participant withdrawal from follow-up.

Example Figure 1: CONSORT flow diagram

4.1.1 Screening, eligibility and recruitment

The representativeness of the study sample will be assessed using the following data (shown in the CONSORT flow diagram):

- The number of patients identified at screening
- The number of patients screened and not meeting eligibility criteria (with reasons)
- The number of eligible patients identified at screening
- The number of eligible patients not taking part in the study (with reasons where available)
- The number of eligible patients randomised into the study

Data will be reported overall and by site. Observed and projected recruitment rates over time will be plotted.

4.1.2 Protocol deviations

Protocol deviations will be captured on a Deviation Tracking Log which will be held centrally by the Newcastle Clinical Trials Unit (NCTU).

Cross-over between treatment groups may occur during the course of this study and is permitted within the protocol; however, clinical teams will be asked to allow sufficient time, and ideally until the primary outcome is assessed at six months, before considering changing allocated treatment. Supplementary reporting of the primary outcome measure may be conducted using only data collected prior to cross-over or treatment discontinuation (see section 3.4). The number of participants changing treatment allocation or prematurely discontinuing their allocated trial treatment will be reported (see section 4.3).

Given the pragmatic nature of this trial we have not pre-specified any major protocol deviations which would affect the validity of the study or have a direct bearing on the primary outcome analysis or analysis populations.

A listing of all reported protocol deviations will be provided to the trial statistician at the end of the study. The number and type of protocol deviations will be summarised by treatment group.

4.2 Baseline characteristics

Baseline characteristics will be summarised descriptively, both overall and by randomised treatment group. Categorical variables will be summarised by frequency and percentage. Continuous data will be summarised by the mean and standard deviation and/or median and range, as appropriate. No significance testing will be carried out due to the randomised nature of the study.

Parts I, II and IV of the Unified Parkinson's Disease Rating Scale (UPDRS) will be completed at baseline for participants with Parkinson's disease, dementia with Lewy bodies or Multi system atrophy. Part I and Part II each comprise 13 questions rated on a 5-point scale from 0 (normal) to 4 (severe). The Part I and Part II subscale scores are calculated by summing the responses to each of the 13 questions to obtain a score ranging from 0 to 52, with higher scores corresponding to worse outcomes. When no more than 20% of items are missing within subscales we will use simple imputation methods by replacing the missing item with the median response from the respondent specific completed questions within the subscale. If more than 20% of items are missing the subscale score will be set as missing. Part IV comprises six questions, rated on a 5-point scale from 0 (normal) to 4 (severe). The Part IV subscale score is calculated by summing the responses to each of the 6 questions to obtain a score ranging from 0 to 24, with higher scores corresponding to worse outcomes. When no more than 20% of items are missing the moment has the median response to a score ranging from 0 to 24, with higher scores corresponding to worse outcomes. When no more than 20% of items are missing the median response from the respondent specific completed questions methods by replacing the missing item with the median response to obtain a score ranging from 0 to 24, with higher scores corresponding to worse outcomes. When no more than 20% of items are missing we will use simple imputation methods by replacing the missing item with the median response from the respondent specific completed questions within Part IV. If more than 20% of items are missing the subscale score will be set as missing.

Details of characteristics to be reported are given in Example Table 2 below.

Example Table 2: Baseline characteristics

Conservative	Conservative management plus	Conservative management plus	Overall
management			Overall
N=	N=	N=	N=
naire (OHO)			
	-		
	1		
	management	management plus fludrocortisone N= N= N=	management plus fludrocortisone management plus midodrine N= N=

Unless otherwise stated data are; ¹ mean (SD) and/or median (range); ² n (%)

³Only completed for participants with Parkinson's disease, dementia with Lewy bodies or Multi system atrophy

4.3 Treatment compliance

Participants will be randomised to receive conservative management, conservative management plus fludrocortisone or conservative management plus midodrine.

Conservative management is standard first-line care and forms the control arm of this study. Conservative management consists of non-pharmacologic therapy and will be implemented according to each site's usual clinical practice. The conservative, non-pharmacological measures advised at baseline will be tabulated by randomised treatment group.

Fludrocortisone and midodrine will be prescribed according to local clinical practice.

Given the pragmatic nature of this study adherence to prescribed medication and non-drug therapies will not be monitored. Participants may cross-over between treatment arms and this will be recorded. Participants who cross-over between treatment groups, or discontinue trial treatment should remain in the trial and be offered all follow-up visits.

The frequency and percentage of participants prematurely discontinuing their allocated trial treatment will be reported along with a reason, where available, and the timing of treatment discontinuation. Whether the participant crossed over to an alternative treatment group will be tabulated, see Example Table 3. Multiple cross-overs between treatment groups will be reported if this occurs.

For each pharmacological intervention (fludrocortisone and midodrine) the number of participants prescribed each treatment (regardless of allocated treatment group) will be reported along with the duration they received the treatment within the 12 month trial period and whether the treatment was prematurely discontinued, with reasons where available. See Example Table 4.

We will also report the frequency and percentage of participants taking 'culprit medications' at baseline and each follow-up visit and any changes to these since the previous visit (started, stopped, dose increased, dose decreased, or no change). This will be reported by randomised treatment group for each type of medication collected in the study database. In addition, for participants with Parkinson's disease, we will calculate the Levodopa equivalent daily dose (LEDD) at baseline and each follow-up visit according to the method proposed by Tomlinson et al [8]. This will be reported in each randomised treatment group as the median and range. See Example Table 5.

Example Table 3: Treatment adherence

	Conservative management N=	Conservative management plus fludrocortisone N=	Conservative management plus midodrine N=
Discontinued allocated treatment			
Yes			
No			
If yes, due to			
Lack of efficacy			
Side effects			
Other reason			
Time from randomisation to			
discontinuation of allocated treatment			
<3 months			
3-6 months			
>6 months			
Crossed over to another treatment			
group			
Yes			
No			
If yes, switched to			
Conservative management	NA		
Conservative management plus		NA	
fludrocortisone			
Conservative management plus			NA
midodrine			

Data are n(%)

Example Table 4: Trial pharmacological treatments received

	Fludrocortisone	Midodrine
Prescribed treatment		
Duration of treatment		
(months)		
Median; Range		
Prematurely discontinued		
treatment		
Yes		
No		
If yes, due to		
Lack of efficacy		
Side effects		
Other reason		

Data are n(%) unless otherwise stated

Example Table 5: Culprit medications

		1	
	Conservative management N=	Conservative management plus fludrocortisone N=	Conservative management plus midodrine N=
	IN-	IN-	IN-
Culprit medication 1*			
Baseline ¹			
Month 3 ¹			
Started since baseline			
Stopped since baseline			
Dose increased			
Dose decreased			
No change			
Month 6 ¹			
Started since Month 3			
Stopped since Month 3			
Dose increased			
Dose decreased			
No change			
Month 12 ¹			
Started since Month 6			
Stopped since Month 6			
Dose increased			
Dose decreased			
No change			
LEDD			•
Baseline			
Number with data			
Median; Range			
Month 3			
Number with data			
Median; Range			
Month 6			
Number with data			
Median; Range			
Month 12			
Number with data			
Median; Range			
incaran, hange			

*Will be repeated for each culprit medication.

¹Will be reported as Number taking at visit / number assessed at visit (%)

5. ANALYSIS METHODS

5.1 Primary outcome measure

5.1.1 Main analysis methods

Analysis Set 1 will be used for analysis (see Section 3.4). All data will be reported according to randomised treatment allocation and all available outcome data will be included.

The OHQ score and change from baseline at each follow-up visit will be summarised descriptively by randomised treatment group. The number with data, mean, standard deviation, median and range will be reported, see Example Table 6a. The OHSAS and OHDAS may also be summarised descriptively.

Example Table 6a: Summary of OHQ scores and change from baseline

	Va	lue at follow-up visi	t	Change from baseline			
OHQ score	Control	Fludrocortisone	Midodrine	Control	Fludrocortisone	Midodrine	
Month 3							
N							
Mean (SD)							
Median (Range)							
Month 6							
N							
Mean (SD)							
Median (Range)							
Month 12							
N							
Mean (SD)							
Median (Range)							

Subject to sufficient numbers with data (at least three participants per group with outcome data), we will also estimate the mean difference in the change in OHQ score from baseline to each follow-up time point between each intervention and control group, see Example Table 6b. This will be reported with a standard deviation and 95% CI. The purpose of this is to inform potential future meta-analyses. No inferences will be drawn from this data.

Example Table 6b: Change in OHQ score - mean difference between groups

	Mean diffe	erence (MD)
OHQ score	Fludrocortisone - control	Midodrine - control
	MD (SD; 95% CI)	MD (SD; 95% CI)
Month 3		
Month 6		
Month 12		

To inform future sample size calculations will we report the correlation (Pearson's correlation coefficient) between baseline and follow-up OHQ scores. This will be reported within each randomised treatment group and overall.

Example Table 6c: Correlation between baseline and follow-up OHQ scores

	Pearson's correlation coefficient					
OHQ score	Control	Fludrocortisone	Midodrine	Overall		
Month 3						
Month 6						
Month 12						

5.1.2 Supplementary analyses

Primary outcome data may also be reported using Analysis Set 2 (see Section 3.4). Data will be reported according to allocated treatment group but data collected after discontinuation of allocated treatment or initiation of non-allocated fludrocortisone or midodrine will be set as missing. This dataset will be reported descriptively as described in section 5.1.1. Data will only be reported in this way if there is at least three participants per group with outcome data at each follow-up visit.

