4.3 Exclusion Criteria

- OH secondary to acute or reversible causes (e.g. haemorrhage, sepsis)
- Use of fludrocortisone or midodrine within the last six months
- Terminal illness or life expectancy < 12 months
- Supine hypertension (where the risks of treatment outweigh the benefits) at baseline
- A known allergy to study medication
- A known contra-indication to fludrocortisone or midodrine which outweighs the potential clinical benefit (i.e. if in usual clinical care the clinician and participant feel the risks outweigh the benefits, they would be excluded)
- Current or planned pregnancy during the trial period, or breast feeding (if randomised to either pharmacological arm the participant, if female and of child-bearing potential, must have a negative pregnancy test [urine beta-human chorionic gonadotropin (β -hCG)] and are required to use a highly effective contraceptive method during the trial).
- Inability to communicate in English
- Inability to comply with the study procedures as specified in the schedule of events.
- Currently taking part in another clinical trial that would interfere with the outcomes of CONFORM-OH (site team to check with the CI and Trial Management Group if in doubt)

NB: Enrolling a patient onto the trial who does not meet the inclusion/exclusion criteria is considered a protocol waiver and is in breach of Regulation 29 (SI 2004/1031) of the Medicines for Human Use (Clinical Trials) Regulations 2004. PROTOCOL WAIVERS ARE NOT PERMITTED.

5. Trial Procedures

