6.1 Description of Conservative Management

For the purpose of this study, non-pharmacologic therapy is referred to as conservative management. Conservative management is standard first-line care and forms the control arm of this trial.

Conservative management may consist of the following:

- Education about the condition
- Trigger avoidance (avoiding dehydration, alcohol, excess caffeine, large meals, hot environments, aerobic exercise and specific personal triggers)
- Safe standing (using the skeletal muscle pump before standing, moving slowly to an upright position, particularly in the morning and the use of counter-manoevres during standing)
- Physical counter-manoevres (these are adapted to an individual's ability and include standing with legs crossed, repeated calf raises and knee bends, tensing legs, abdominals and buttocks. Some sites may use biofeedback to demonstrate the efficacy of these manoeuvres during BP monitoring. Study sites will continue to perform their usual clinical practice)
- Fluid and salt intake (avoid dehydration, bolus-water drinking, at least 10 g (two teaspoons) of salt per day)
- Compression hosiery (Grade 2 full leg length compression stockings and/or abdominal binder)

The specific conduct of conservative management will vary between sites. Conservative management will begin following diagnosis, as is usual clinical practice.

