6.8 Concomitant Medications

It is anticipated that the majority of participants will be taking multiple medications. There are no absolute contra-indications to other medications. Local research teams should follow their usual clinical practice and consult the BNF to review cautions and contra-indications. In line with clinical guidelines, clinicians will be required to review those medications known as 'culprit medications'. These could cause or worsen OH, and are as follows: alpha-blockers, beta-blockers, Calcium channel blockers, diuretics, ACE-inhibitors, Angiotensin II Receptor blockers, Nitrates (regular, not PRN), other vasodilators (eg sildenafil, nicorandil), other anti-hypertensives (eg clonidine), tricyclic anti-depressants, dopamine agonists, SSRI anti-depressants, anti-psychotics, Levodopa, Monoamine oxidase inhibitors (MAOI), and catechol-o-methyltransferase (COMT) inhibitors [1, 17, 32]. Other current treatments for OH that should be checked for at each visit are atomoxetine, pyridostigmine, octreotide and desmopressin. A risk/benefit decision will be made by the participant and clinician (as would be usual clinical practice), whether to discontinue, modify or continue any of these medications. Given the pragmatic nature of the trial, participants may still enter the study if they continue 'culprit' medication(s); Culprit medications should be reviewed at each trial visit and document any changes in the participants medical record and eCRF.

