3.4 Analysis sets

The following analysis sets will be defined:

Analysis Set 1	 Participants will be analysed according to the treatment group they were randomised to receive, i.e. following the intention-to-treat (ITT) principle All available outcome data will be included in the analysis
Analysis Set 2	 Participants will be analysed according to the treatment group they were randomised to receive, i.e. following the intention-to-treat (ITT) principle Outcome data following cross-over to an alternative treatment group, or discontinuation of allocated trial treatment, will be set to missing
Safety Analysis Set (SAS)	 For each treatment group, the Safety Analysis Set will comprise all participants exposed to that treatment strategy Safety data (adverse events) will be summarised according to the treatment strategy received at the time of onset of each adverse event. Participants who cross-over between treatment groups will be included in the Safety Analysis Set for each treatment group

Primary and secondary clinical outcome measures will be reported according to randomised treatment group; safety data will be reported according to the treatment strategies received. Analysis Set 1 will be the main analysis set used to report the primary and secondary clinical outcome measures. Analysis Set 2 may also be used to provide supplementary information on the primary outcome measure. All safety data will be reported using the Safety Analysis Set.

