- 2) The main analysis would use all OHQ data reported at the three, six and 12-month visits. If >10% of questionnaires, either overall or within any arm, were completed outside of the protocol specified visit windows we would repeat the analysis excluding these data.

iv. Supplementary analyses

A supplementary analysis would be performed targeting an 'on-treatment' or hypothetical estimand; the treatment effect if all participants had continued on their allocated treatment. The key aspects of this estimand are described in the table below:

Estimand attribute	Description		
Population	Patients with symptomatic OH refractory to lifestyle modification		
	and meeting the CONFORM-OH eligibility criteria		
Treatment	Six months of treatment with conservative management plus		
	fludrocortisone or conservative management plus midodrine		
	compared to conservative management alone		
Outcome variable	Overall composite OHQ score at month six		
Strategies used to handle	Discontinuation of allocated treatment – hypothetical ¹		
intercurrent events	Use of non-allocated treatment with fludrocortisone or		
	midodrine – hypothetical ¹		
Population-level summary	Mean difference in OHQ score at six months (adjusted for baseline)		
measure	between the intervention and control groups		

¹ Under a **hypothetical** strategy we are interested in the value the outcome variable would have taken had the intercurrent event not happened

This analysis would be performed using Analysis Set 2 (see Section 3.4). Participants would be analysed according to their allocated treatment group but data collected after discontinuation of allocated treatment or initiation of non-allocated fludrocortisone or midodrine would be set as missing. This dataset would be analysed using the same linear mixed-model as described above (*i. Main analysis methods*). The model assumes data are missing at random, i.e. that the missing data would be similar to that of other participants in the same treatment group with similar baseline characteristics.

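### Analysis Set 2 and the on-treatment estimand do not count starting another OH drug named in protocol 6.8 as leaving allocated treatment

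*SAP*

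**What the plan says.** **The rule.** SAP 3.4 defines Analysis Set 2: "Outcome data following cross-over to an alternative treatment group, or discontinuation of allocated trial treatment, will be set to missing". SAP 5.1.2 restates this with named drugs: "data collected after discontinuation of allocated treatment or initiation of non-allocated fludrocortisone or midodrine will be set as missing". SAP Appendix B.a.iv repeats it for the full-size trial ("data collected after discontinuation of allocated treatment or initiation of non-allocated fludrocortisone or midodrine would be set as missing"), and its estimand table lists the same two intercurrent events under a hypothetical strategy. The target is "the treatment effect if all participants had continued on their allocated treatment". Protocol 8.1 (Efficacy Analysis Population 2) also refers only to cross-over to another group or discontinuation.

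**The control strategy.** Protocol 6.1: "For the purpose of this study, non-pharmacologic therapy is referred to as conservative management".

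**The other drugs.** Protocol 6.8: "Other current treatments for OH that should be checked for at each visit are atomoxetine, pyridostigmine, octreotide and desmopressin". The prior-drug exclusion in protocol 4.3 covers only "Use of fludrocortisone or midodrine within the last six months".

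**Reporting.** Example Table 3 offers the three trial strategies as the only switch destinations. Example Table 4 covers fludrocortisone and midodrine. Example Table 5 covers culprit medications, with rows for drugs started since the previous visit.

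**The concern.** The protocol treats the four drugs as treatments for the same condition and has sites look for them at every visit, but the SAP never names them. If a control participant starts midodrine, later OHQ scores are removed from Analysis Set 2. If the same participant starts pyridostigmine instead, the scores stay in as the outcome of non-drug management. The same gap lets an add-on in a drug arm count as part of the allocated drug's effect.

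At stake is whether the supplementary result means what its estimand says. A symptom score reached with the help of an unallocated OH drug is not the score that would have been seen on allocated treatment alone.

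**Working it through.** **1. Does any statement of the rule cover the four drugs?**
- SAP 5.1.2 and Appendix B.a.iv: the triggers are discontinuation, or starting non-allocated fludrocortisone or midodrine. Not covered.
- SAP 3.4 and protocol 8.1: the triggers are cross-over to another group, or discontinuation. The groups are the three trial strategies, so starting a fourth drug is not a cross-over. Not covered.
- Example Table 3: there is no destination for such a drug.

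**2. Are the drugs kept out in some other way?** No. Protocol 4.3 does not exclude them, protocol 6.8 leaves medication decisions to clinician and participant, and protocol 6.9.1 allows combination treatment to be considered.

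**3. Does the main estimand have the same problem?** No. Appendix B.a.i defines it as the effect of allocation whatever other treatment is received. Its table lists only the two events, but the definition already includes these drugs.

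**4. Reproducing the plan's own figure.** Inputs from SAP 2.6: difference 1.0, SD 2.2, two-sided 5%, power 90%.
- n per arm = 2 × (1.960 + 1.282)² × 2.2² / 1.0² = 101.7, so 102 by the normal approximation.
- Noncentral-t power is 89.8% at 102 and 90.1% at 103, so the stated 103 is right.
- 103 / 0.85 = 121.2, so 122 per arm, and 3 × 122 = 366, as stated.

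No design figure changes.

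**5. Direction.** Higher OHQ is worse, so write benefit as control mean minus drug mean. Let fractions f_C (control) and f_D (drug arm) of the retained participants take another OH drug that lowers OHQ by e. Then

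observed difference = 1.0 − e × (f_C − f_D).

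With e = 1.0:
- f_C = 10%, f_D = 0 gives 0.90.
- f_C = 0, f_D = 10% gives 1.10.
- f_C = f_D gives 1.00.

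The sign of the net shift depends on two rates that the documents do not give.

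**6. Illustrative size, control use only.** Both f_C and e are assumptions. Power is noncentral-t at 103 per arm with SD 2.2, starting from 90.1%.

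| f_C | difference, e = 0.5 to 1.0 | power |
|---|---|---|
| 5% | 0.975 to 0.95 | 88.6% to 87.0% |
| 10% | 0.95 to 0.90 | 87.0% to 83.2% |
| 20% | 0.90 to 0.80 | 83.2% to 73.8% |
| 30% | 0.85 to 0.70 | 78.8% to 62.3% |

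This is the one-sided case. Add-on use in the drug arms would offset it.

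**7. The closed trial.** One affected control among m shifts the control mean by e/m. For m = 3 this is 0.5/3 = 0.17 to 1.0/3 = 0.33 points; for m = 10 it is 0.05 to 0.10.

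**The case against.** **Starting a drug is itself discontinuation of control.** Since control is non-pharmacologic, any OH drug arguably ends it. But discontinuation is not defined for the control arm, and a participant can add a drug and keep the conservative measures. If any added drug counted, naming fludrocortisone and midodrine would be redundant for controls. In the drug arms an add-on is plainly not discontinuation. What stands is that the text is ambiguous for control.

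**The stakes are small.** This stands. The trial closed in its pilot phase for very low recruitment (SAP 1.1), and the hypothetical estimand sits only in an Appendix of analyses that will not be run. The Analysis Set 2 report is optional, untested, and needs at least three participants per group with data at each visit.

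**Such use may be rare.** SAP 1.1 describes fludrocortisone and midodrine as the two drug options when lifestyle measures fail. A control participant doing badly may well be given one of those, and Analysis Set 2 already removes those scores. This limits the plausible f_C but does not close the gap.

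**A reader might infer bias towards zero for both drugs.** The documents do not support that, because add-on use in the drug arms pushes the other way (step 5).

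**A reader might infer that the treatment-policy result is compromised.** It is not. Its definition covers any other treatment received, although counts of such use would help in reading it.

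**A reader might infer that use of these drugs will go unreported.** That cannot be established. SAP 4.3 reports each medication type held in the study database by arm, and Example Table 5 has rows for new starts. If the database holds these drugs they may appear there, though under a culprit label.

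**Setting these scores to missing has its own bias.** This stands. SAP 5.4 plans no imputation in the live report, so removing controls who started a drug because they were doing badly may also flatter the control mean. The existing fludrocortisone and midodrine rule carries the same weakness, so it is no reason to treat the four drugs differently.

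**Conclusion.** The point holds as a mismatch of definition. Every statement of the Analysis Set 2 rule omits OH treatments that the protocol itself names, so scores obtained with them count as outcomes of the allocated strategy, contrary to the estimand's stated target. It applies to all three arms.

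The net bias has no known sign or size. The figures in step 6 rest on assumed usage (5% to 30% of controls), an assumed effect (0.5 to 1.0 points) and no use in the drug arms; none of these comes from the documents. The main treatment-policy estimate and the sample size are unaffected. In the closed trial the consequence is confined to the optional Analysis Set 2 summary and the mean differences derived from it, which SAP 5.1.1 offers for future meta-analyses. This is a cheap improvement, not a threat to the main report.

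**What to change.** - In SAP 3.4, 5.1.2 and the hypothetical estimand table in Appendix B.a.iv, widen the event to: *start of non-allocated fludrocortisone or midodrine, or start after randomisation of another OH treatment listed in protocol 6.8*. Set later OHQ scores to missing in Analysis Set 2.
- In the main estimand table (Appendix B.a.i), name these drugs under the treatment policy strategy, so that the table matches its own definition.
- Tabulate new starts and baseline use of the four drugs by randomised arm, separately from culprit medications. Use already present at baseline is described, not treated as an event.

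This changes analysis and reporting only, not who may receive which drug.

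**Cost.** The SAP wording is short, but someone must confirm that the database holds start dates, or at least use at each visit: protocol 6.8 asks sites to check for these drugs, which does not prove that dates are captured. A few more values become missing in Analysis Set 2, possibly from participants with worse symptoms, and the live report does not impute them. With exactly three participants in a group, removing one leaves two, below the SAP's minimum, and the Analysis Set 2 report would then not be produced.
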